CIAS	cognitive impairment associated with schizophrenia
C _{max}	maximum observed plasma concentration
C _{min}	minimum plasma drug concentration
CNS	central nervous system
CRF	case report form
eCRF	electronic case report form
CSF	cerebrospinal fluid
C _{ss,av}	average steady-state drug plasma concentration
C-SSRS	Columbia-Suicide Severity Rating Scale
CV	coefficient of variation
CYP	cytochrome P450
DNA	deoxyribonucleic acid
DSM-5	Diagnostic and Statistical Manual of Mental Disorders, 5 th edition
EC	ethics committee
ECG	electrocardiogram
EDCMS	electronic data capture and management system
██████████	██████████
EQ-VAS	Euroqol-Visual Analog Scale

ERP	Event-related potential
ET	early termination
EU	European Union
FDG	2-deoxy-2-[¹⁸ F]fluoro-D-glucose
fMRI	functional magnetic resonance imaging
HIV	human immunodeficiency virus
IA	Interim analysis
ICH	International Council for Harmonisation
ID	identification
IDMC	independent data monitoring committee
IQ	intelligence quotient
IRB	institutional review board
IRT	interactive response technology
ITT	intent to treat
LNS	letter number sequencing
MAD	multiple ascending dose
MAR	missing at random
MATRICS	Measurement and Treatment Research to Improve Cognition in Schizophrenia
MCCB	MATRICS Consensus Cognitive Battery
MGH	Massachusetts General Hospital
MHP	mental health professional
MINI	Mini-International Neuropsychiatric Interview for Psychotic Disorders
MMRM	mixed model repeated measures
MTD	maximum tolerated dose
NMDA	N -methyl-D-aspartate
NMDAR	N -methyl-D-aspartate receptor
NOAEL	no observable adverse effect level
NOEL	no observable effect level
NPI	Neuropsychiatric Inventory
PANSS	Positive and Negative Syndrome Scale
PD	pharmacodynamics
QD	once daily
QTcF	QT interval corrected for heart rate using Fridericia's correction
RNA	ribonucleic acid
SAE	serious adverse event
SAFER (criteria)	State versus trait, Accessibility, Face validity, Ecological validity, Rule of 3 Ps (pervasive, persistent, and pathological)
SAP	statistical analysis plan

SARA	Scale for the Assessment and Rating of Ataxia
SCI-PANSS	Structured Clinical Interview for Positive and Negative Syndrome Scale
SCID	Structured Clinical Interview for DSM disorders
SCoRS	Schizophrenia Cognition Rating Scale
[REDACTED]	[REDACTED]
SD	standard deviation
SM	safety margin
TID	3 times daily
[REDACTED]	[REDACTED]
UCSD	University of California, San Diego
ULN	upper limit of normal
US	United States
UPSA-Bi	UCSD Performance-Based Skills Assessment – Brief, international version
WRAT4-R	Wide Range Achievement Test 4 – Reading

1. DESCRIPTION OF OBJECTIVES AND ENDPOINTS

1.1 Primary Objective and Endpoints

The primary objective of the study is to evaluate the efficacy of BIIB104 in subjects with cognitive impairment associated with schizophrenia (CIAS), using the Working Memory Domain of the MATRICS Consensus Cognitive Battery (MCCB).

The primary endpoint that relates to this objective is the change from baseline in MCCB Working Memory Domain score to Week 12.

1.2 Secondary Objectives and Endpoints

The secondary objectives are:

[figure not shown]
- To evaluate the safety and tolerability of BIIB104 in subjects with CIAS.
- To evaluate the efficacy of BIIB104 in subjects with CIAS on measures of cognition, functioning, and psychiatric symptomology, as measured by:
 - University of California, San Diego Performance Based Skills Assessment–Brief, international version (UPSA-Bi)
 - Schizophrenia Cognition Rating Scale (SCoRS)
 - MCCB
 - Positive and Negative Syndrome Scale (PANSS)
 - Clinical Global Impression–Severity (CGI-S) and Clinical Global Impression Improvement (CGI-I).

The secondary endpoints are:

- Incidence of adverse events (AEs) and serious adverse events (SAEs) reported during the study, Scale for the Assessment and Rating of Ataxia (SARA), Columbia–Suicide Severity Rating Scale (C-SSRS)
- Change from baseline in UPSA-Bi assessment to Week 12
- Change from baseline in SCoRS assessment to Week 12
- Change from baseline in MCCB Composite and Individual Domain scores (excluding Working Memory Domain) to Week 12
- Change from baseline in PANSS total score, and subscale scores to Week 12
- Change from baseline in CGI-S to Week 12
- CGI-I at Week 12

Figure 1. The two panels of the visual search task.

For more information, contact the Office of the Vice President for Research and Economic Development at [contact] or [contact].

- 

1

1

1

• 1

1000

Page 1 of 1

1

1. **What is the primary purpose of the study?** (1 point)

1

1

Page 10 of 10

1

1

1

10

10

1

1

• 1

1

2. STUDY DESIGN

2.1 Study Overview

This is a Phase 2, randomized, double-blind, placebo-controlled, parallel-group study to evaluate the safety, tolerability, and efficacy of BIIB104 in subjects with CIAS. Approximately 219 male and female subjects with stable schizophrenia from age 18 to 55 years, inclusive, will be recruited. Dosing with BIIB104 0.15 mg BID and 0.5 mg BID versus placebo BID will be evaluated over a treatment phase of 12 weeks. The study will be conducted at approximately 80 sites globally including non-English speaking countries.

The study includes a screening phase, a placebo lead-in phase, a randomized treatment phase, and a safety follow-up (SFU) phase to begin after the last dose of study treatment.

Screening evaluation will occur up to 35 days prior to randomization. Once eligibility has been established, a 7-day Placebo Lead-In evaluation will be conducted to assess the subject's ability to comply with dosing requirements. After Sponsor confirmation of eligibility and completion of baseline measurements at the Baseline/Day 1 Visit, subjects will be randomized in a 1:1:1 ratio to receive BIIB104 0.5 mg, BIIB104 0.15 mg, or placebo. Subjects will be dosed at approximately 12-hour intervals for 12 weeks. Total duration of subject participation will be approximately 19 weeks from screening to final follow-up visit.

[figure not shown]
There are 3 treatment groups and subjects are randomized in a 1:1:1 ratio into 1 of 3 treatment groups. The randomization will be stratified by region.

Table1: Treatment groups

Treatment Groups	Description
Placebo group	Up to 73 subjects to receive oral dosing BID with placebo for 12 weeks.
BIIB104 0.15 mg group	Up to 73 subjects to receive oral dosing BID with BIIB104 0.15 mg for 12 weeks
BIIB104 0.5 mg group	Up to 73 subjects to receive oral dosing BID with BIIB104 0.5 mg for 12 weeks

2.2 Study Schematic

Figure 1: study design

N = number of subjects; MCCB = MATRICS Consensus Cognitive Battery; BID = twice daily.

*Note: The Placebo Lead-In evaluation may begin any time after eligibility has been established based on screening assessments, provided that the Placebo Lead-In is completed no earlier than 3 days prior to the Baseline/Day 1 Visit.

2.3 Schedule of Events

See protocol section 5.

3. SAMPLE SIZE JUSTIFICATION

The protocol states that:

Fifty-one subjects per treatment group will have approximately 80% power to detect a true mean difference of 3.5 in change from baseline MCCB Working Memory Domain score to Week 12 between the treatment and placebo groups. With the assumed drop-out rate of 30%, 73 subjects are required from each group to maintain the 80% power. This power calculation is based on a 2-

sided *t*-test assuming equal variance with a final significance level of 0.1, and a standard deviation of 7. The statistical software EAST 6.3® is used for sample size calculation. The sample size may be re-estimated based on blinded data review and evolving development of the study.

4. STATISTICAL ANALYSIS METHODS

4.1 General Considerations

This statistical analysis plan (SAP) describes the planned analyses for this phase 2 study evaluating the primary, secondary [REDACTED] objectives. This SAP also covers the planned interim and final analyses, and therefore there is no separate SAP for the interim analysis.

Data listings will be provided by treatment group, visit, and subject, if applicable. Summary statistics and statistical analyses will only be presented for data where detailed in this SAP. For continuous data, summary statistics will include the arithmetic mean, arithmetic standard deviation (SD), median, minimum (Min), maximum (Max) and n; for log-normal data the geometric mean and geometric coefficient of variation (CV) will also be presented. For categorical data, frequency count and percentages will be presented. Data listings will be provided for all subjects up to the point of withdrawal, with any subjects excluded from the relevant population highlighted. Summary statistics and statistical analyses will generally only be performed for subjects included in the relevant analysis population.

Data will be summarized and presented by treatment group, defined in Table 1. Data will be listed by treatment group. Exposure to study medication will be tabulated by treatment group.

Unless stated otherwise, baseline data are defined as the data collected prior to the time and/or on the day of the first dose, which is usually the same day as the Day1/Baseline visit. If data are not available on Day 1 for safety assessment, the measurements recorded up to 3 days prior to first dose (i.e. Day -3) will be used as baseline. For efficacy assessments, the Day1/Baseline visit may be performed over 2 days, i.e., on Day 1 and Day 2. Therefore, an assessment performed on the second day of visit Day1/Baseline (i.e., Day 2), will be used as baseline if not already performed on the first day of visit Day1/Baseline (i.e., Day 1). If there is more than one value on/before the day of the first dose, the non-missing value closest to and prior to the first dose will be used as the baseline value

Unless stated otherwise, all statistical tests will be 2-sided with statistical significance level of 0.10.

The statistical software, SAS 9.4®, will be used for all summaries and statistical analyses.

4.1.1 Analysis Population

- Intent-to-treat (ITT) population:

The ITT population is defined as all randomized subjects who received at least one dose of study treatment (BIIB104 or placebo). Subjects will be in the treatment group to which they were randomized in statistical analyses based on the ITT population.

- Per-protocol (PP) population:

The PP population is defined as all subjects in the ITT population who do not have major protocol deviation(s) that impact efficacy. Exclusion of subjects from the PP population will be determined by the SMT members including but not limited to medical director, clinical pharmacologist and biostatistician. The main reasons for exclusion will be documented.

- Safety population:

The safety population is defined as all randomized subjects who received at least 1 dose of study treatment (BIIB104 or placebo). Subjects will be in the treatment group they received in statistical analyses based on the safety population.

- [REDACTED]

4.2 Imputation of Partial Dates for Adverse Events and Concomitant Medication

Partial start dates (of intervention or event):

- Case 1, day is missing (only month and year are present):
 - If year and month are same as treatment period start date, then assign the day of treatment period start date to the partial date. **[worst case scenario (WCS)]**
 - However, if end date of event or intervention is clearly before treatment period start date, assign day '01' to partial start date. **[Max Duration]**
 - Otherwise, assign day of '01' to partial start date. **[Max Duration]**
- Case 2, only year is present:
 - If year is same as treatment period start date, then assign the month and day of the treatment period start date to the partial date. **[WCS]**
 - However, if end date of event or intervention is clearly before treatment period start date, assign 'Jan. 01' to partial start date. **[Max Duration]**
 - Otherwise, assign the month and day of 'Jan. 01' to partial start date. **[Max Duration]**
- Case 3, completely missing date, no imputation is performed.

Partial end dates (of intervention or event):

- Case 1, day is missing (only month and year are present):
 - If year and month are same as study end date, then assign the day of the study end date to the partial date. **[Do not exceed study end]**
 - Otherwise, assign day of last day of the month (28, 29, 30 or 31) to the partial end date **[Max Duration]**
- Case 2, only year is present:
 - If year is same as study end date, then assign the month and day of the study end date to the partial date. **[Do not exceed study end]**
 - Otherwise, assign ‘Dec. 31’ to the partial end date. **[Max Duration]**
- Case 3, completely missing date, no imputation is performed.

If any partial dates have missing month, with day present, then day is ignored and considered missing. The year-only scenario is considered for imputation purposes.

Also, if the study is ongoing (e.g., interim analysis) and study end date is not available then the cut-off date will be used in the place of study end date. If both a cut-off date and study end date are present for a patient, then the minimum of the two dates will be used as the study (or reference) end date.

4.3 Background Characteristics

The summaries in this section will be based on the ITT population. Unless otherwise specified, summary tables will be presented by treatment group (BIIB104 0.15mg, BIIB104 0.5mg, and placebo). All the listing will be presented by treatment group.

4.3.1 Accounting of Subjects

Accounting of subjects will include number (%) of subjects randomized and dosed, number (%) of subjects who completed the treatment/study, number (%) of subjects who discontinued treatment, and number (%) of subjects who withdrew from study. For subjects who discontinued treatment, the reasons for treatment discontinuation and the number of days on treatment will be summarized. For subjects who withdrew from the study, the reasons for withdrawal and the number of days on the study will be summarized. Time to treatment discontinuation and time to study withdrawal will be displayed by Kaplan-Meier plots.

Accounting of subjects will be also summarized in each analysis population.

4.3.2 Demographics and Baseline Characteristics

The demographic information of age, gender, ethnicity, race, height, weight, smoking status, and body mass index (BMI) will be summarized by treatment group. By-subject listings of such information will be provided.

The categorization of regions is determined from geography, language and culture from each country. The region category will be used as a covariate in statistical models and in subgroup analyses as appropriate.

Baseline clinical assessment variables include baseline MCCB domains, MCCB overall composite score, MCCB neurocognitive composite score, UPSA-Bi, SCoRS, PANSS total score, PANSS Positive Scale, PANSS Negative Scale, PANSS General Psychopathology Scale, SARA, C-SSRS, and CGI-S. Number of years since first episode of schizophrenia, age of first treatment of schizophrenia, number of previous episodes or exacerbations of schizophrenia in the last 24 months, and number of past psychiatric hospitalizations will also be summarized.

Medical history will be coded using the latest version of the Medical Dictionary for Regulatory Activities (MedDRA). The number (%) of subjects with history (including both ongoing and not ongoing medical conditions) will be summarized by system organ class and preferred term. A listing of medical history will be generated.

4.3.3 Concomitant Medications and Antipsychotic Treatment

Concomitant medications will be coded using the latest version of the World Health Organization (WHO) medication dictionary. Concomitant non-drug treatments will be coded using the latest version of the Medical Dictionary for Regulatory Activities (MedDRA). A concomitant medication could be taken on or after the day of the first dose of study drug. This includes concomitant medications that start prior to the initiation of the first dose if their use continues or after the date of first dose. An antipsychotic treatment is any treatment for CIAS that is ongoing at the time of trial entry.

To define concomitant use for therapies or antipsychotic treatments with missing start or stop dates, the following additional criteria will be used:

- If both the start and stop dates of a therapy are missing, then the therapy will be considered concomitant;
- If the start date of a therapy is missing and the stop date of that therapy falls on/after the first dose date, the therapy will be considered concomitant;

- If the start date of a therapy is prior to the date of the first dose and the stop date of the therapy is missing and the therapy is listed as ongoing, that therapy will be considered concomitant;
- If the start date of a therapy is prior to the date of first dose and the stop date of that therapy is missing and the therapy is not listed as ongoing, the therapy will be considered non-concomitant.
- If start date of a therapy is after the last dose date but before the end of study date, the therapy will be considered concomitant.

The number and percent of subjects taking concomitant medication, non-drug treatments and antipsychotic treatment will be summarized by treatment group.

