4.1. Schizophrenia and Cognitive Defects

Schizophrenia is a chronic, highly debilitating psychiatric disorder with a point prevalence worldwide ranging from 2.7 to 8.3 per 1000 population [Eaton and Chen 2006]. Schizophrenia includes positive symptoms (hallucinations, paranoia, delusions), negative symptoms (apathy, alogia, affective flattening), and cognitive symptoms (deficits in memory, attention, executive function) [Javitt and Laruelle 2006]. At an individual level, almost all patients with schizophrenia have cognitive impairments relative to what would be expected had they never developed schizophrenia [Kremen 2000]. Impaired cognition is now seen as a feature of schizophrenia that precedes, accompanies, and then outlasts a patient's symptoms and medical regimen [Heinrichs 2005]. Measurable deficits in thought and language, perception, memory, and attention appear in vulnerable children long before psychosis appears [Erlenmeyer-Kimling

CONFIDENTIAL

The information contained herein may not be used, disclosed, or published without the written consent of Biogen MA Inc.

2000]. Patients experiencing their first psychotic episodes are cognitively impaired, and this impairment is relatively stable over time [Albus 2002]. Studies suggest little or no relation between symptoms and cognitive performance early in the illness, and cognitive deficits remain when symptoms remit in response to treatment [Hughes 2003; Rund 2004]. Thus, neurocognitive deficits do not correlate with positive symptom severity and only modestly correlate with negative symptom severity ($r=0.13-0.27$) [Keefe 2006].

Effective treatment of cognitive deficits in schizophrenia remains a critical unmet medical need. Current antipsychotic treatments most effectively treat positive symptoms, modestly improve negative symptoms, and have little to no effect on the cognitive deficits [Keefe 2007; Stroup 2006]. Effective treatment of cognitive deficits would enable patients with schizophrenia to live more fulfilling and productive lives in society.

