4.2. Current Therapies for CIAS

Currently, there are no approved pharmacological treatments for CIAS.

CONFIDENTIAL

The information contained herein may not be used, disclosed, or published without the written consent of
Biogen MA Inc.

[REDACTED]

[REDACTED]

[REDACTED]

[REDACTED]

[REDACTED]

[REDACTED]

CONFIDENTIAL

The information contained herein may not be used, disclosed, or published without the written consent of
Biogen MA Inc.

[REDACTED]

[REDACTED]

[REDACTED]

[REDACTED]

[REDACTED]

[REDACTED]

CONFIDENTIAL

The information contained herein may not be used, disclosed, or published without the written consent of
Biogen MA Inc.

CONFIDENTIAL

The information contained herein may not be used, disclosed, or published without the written consent of
Biogen MA Inc.

The image consists of a series of horizontal black bars on a white background. There are approximately 10-12 bars in total. The bars are of varying widths and are positioned at different heights. Some bars are longer and centered, while others are shorter and located towards the top or bottom of the frame. The bars are thick, suggesting they are composed of multiple pixels. The overall pattern is a staggered, non-overlapping arrangement of horizontal lines.

Additional information about BIIB104 may be found in the Investigator's Brochure.

CONFIDENTIAL

CONFIDENTIAL
The information contained herein may not be used, disclosed, or published without the written consent of Biogen MA Inc.

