8. SELECTION OF SUBJECTS

8.1. Inclusion Criteria

To be eligible to participate in this study, candidates must meet the following eligibility criteria at the time of randomization, or at the timepoint specified in the individual eligibility criterion listed:

1. Evidence of a personally signed and dated informed consent document at the time of Screening indicating that the subject has been informed of all pertinent aspects of the study.
2. Evidence of a personally signed and dated informed consent for the informant indicating the informant has been informed of all pertinent aspects of the study. Informant consent must be signed prior to the in-person informant interview conducted during Screening.
3. Otherwise healthy male and/or female subjects from age 18 to 55 years, inclusive, with a Diagnostic and Statistical Manual of Mental Disorders, Fifth Edition (DSM-5), diagnosis of schizophrenia of at least 2 years duration as confirmed by the MINI 7.0.2 for Psychotic Disorders. The MINI 7.0.2 for Psychotic Disorders will also be used to exclude comorbid diagnoses. In addition, diagnosis of schizophrenia must be deemed “valid” by remote, independent raters using prespecified criteria (see Section 9.1.1.3).
4. Evidence of stable schizophrenia symptomatology ≥ 12 weeks (e.g., no hospitalizations for schizophrenia, no increase in level of psychiatric care due to worsening of schizophrenia symptoms).
5. Subjects must be receiving ongoing maintenance atypical antipsychotic therapy (except clozapine), on a stable treatment regimen for ≥ 8 weeks prior to Baseline/Day 1, including concomitant psychiatric medications. Doses of background atypical antipsychotics should be within the recommended dose range listed in the approved product labeling of the country where the study is being conducted. Doses exceeding the recommended dose range are not permitted and doses below the recommended dose range should be discussed with the Sponsor's Medical Monitor (see Section 11.4.1).
 - Treatment regimen stability is defined as maintaining the same dosage of treatments except for minor adjustments ($\leq 25\%$) to manage medication-specific tolerability issues. Recognizing that physicians outside of the study may be managing the subject's background antipsychotic and other psychiatric medications, changes in background antipsychotic and psychiatric medications should be discussed with the Sponsor's Medical Monitor.

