24. Use of prohibited treatments (see Section 11.4.1) and inability to discontinue these concomitant treatments after the Screening Visit. These treatments must be discontinued (or tapered if medically indicated) for a minimum of 5 half-lives prior to randomization at the Baseline/Day 1 Visit. Note that psychiatric medications (excluding psychiatric medications prescribed for non-psychiatric conditions and hypnotics) cannot be

CONFIDENTIAL

The information contained herein may not be used, disclosed, or published without the written consent of Biogen MA Inc.

discontinued to address this criterion due to the treatment regimen stability requirements listed in inclusion criterion 5, above.

25. Use of concomitant treatment that can impair cognition, (e.g., centrally acting antihistamines) as determined by the Investigator in consultation with the Sponsor.
26. Use of concomitant treatment with a significant risk associated with seizures (see Section 11.4.1).
27. Use of typical antipsychotic treatments, including prochlorperazine, haloperidol, loxapine, thioridazine, molindone, thiothixene, pimozide, fluphenazine, trifluoperazine, chlorpromazine, and perphenazine. This list is not all inclusive; the Investigator should discuss the use of any concomitant treatment associated with typical antipsychotic treatments with the Sponsor's Medical Monitor prior to randomizing a subject.
28. Use of off-label treatments for schizophrenia (including, but not limited to, donepezil and modafinil).
29. Screening laboratory test results that deviate from the upper or lower limits of the reference range, except for nonclinically significant values, as determined by the Investigator in consultation with the Sponsor's Medical Monitor, including the following:
 - Aspartate aminotransferase (AST) and alanine aminotransferase (ALT) must be ≤ 2 times the upper limit of reference range, and total bilirubin must be ≤ 1.5 times the upper limit of the reference range at screening.
 - Impaired renal function at screening (e.g., repeated values of creatinine and blood urea nitrogen [BUN] $\geq 1.5 \times$ upper limit of normal (ULN) or estimated glomerular filtration rate [GFR] < 45 mL/min/1.73 m² and corroborating medical history and physical examination). See the Study Laboratory Manual for details of GFR calculation.

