Prohibited treatments must be washed out for a minimum of 5 half-lives of the treatment prior to randomization. Allowable exceptions to this rule include the following:

- The as-needed treatment of anxiety or agitation with up to 2 mg/day lorazepam (or the equivalent dose of another short-acting benzodiazepine) with the following restrictions:
 - Not used within 8 hours of neurological assessments (e.g., neurological examination, SARA) or within 12 hours of scheduled efficacy assessments (e.g., MCCB, SCI-PANSS, UPSA-Bi, SCoRS).
- The as-needed treatment of insomnia with nonbenzodiazepine hypnotics (e.g., zolpidem up to 10 mg/day, zaleplon up to 20 mg/day, eszopiclone up to 3 mg/day) are permitted within their respective recommended dose ranges with the following restriction:
 - Not to be used within 12 hours of scheduled efficacy assessments.
- Minor adjustment ($\leq 25\%$ of the baseline dose) of the dosage of background atypical antipsychotics or psychiatric medications for tolerability. This option should be used only if required to support a subject's continued participation in the study. All efforts should be made to maintain background pharmacotherapy at consistent doses throughout the treatment phase of the study. Recognizing that physicians outside of the study may be managing the subject's background atypical antipsychotic and other psychiatric medications, changes in background medication dosing that exceed this limit should be discussed with the Sponsor's Medical Monitor to determine subject disposition.
- As-needed treatment with any other nonprohibited treatment with potential psychotropic effects (e.g., centrally acting antihistamines) should not occur within 12 hours of scheduled efficacy assessments.
- Acetaminophen and nonsteroidal anti-inflammatory medications may be used intermittently throughout the study.

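### SAP 4.3.3 defines background antipsychotic treatment by the wrong indication (CIAS), so a literal reading leaves the required background drugs out of the by-arm antipsychotic summary

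*SAP*

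**What the plan says.** SAP 4.3.3 plans by-arm counts and percentages of subjects for three categories: concomitant medication, non-drug treatment and antipsychotic treatment. The third is defined in one sentence: "An antipsychotic treatment is any treatment for CIAS that is ongoing at the time of trial entry". The section does not say what date counts as trial entry.

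The protocol describes the background drugs differently:

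- Section 4.2, on the target condition: "Currently, there are no approved pharmacological treatments for CIAS".
- Section 4.1, on what antipsychotics do: "Current antipsychotic treatments most effectively treat positive symptoms, modestly improve negative symptoms, and have little to no effect on the cognitive deficits".
- Section 8.1, criterion 5: "Subjects must be receiving ongoing maintenance atypical antipsychotic therapy (except clozapine), on a stable treatment regimen".

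SAP 4.3.3 separately treats as concomitant any medication taken on or after the day of first dose, including one begun earlier and continued. These medications are coded with the WHO dictionary.

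**The concern.** The SAP sentence attaches the trial's target indication to a drug class given for a different reason. By the protocol's own account, the set of treatments for CIAS ongoing at entry should be almost empty, while the set of antipsychotics ongoing at entry should include every subject. The definition therefore does not describe what it names.

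BIIB104 is tested on top of antipsychotic therapy. A reader of the study report will want to see which background agents were used and whether they were balanced across arms before interpreting working memory or PANSS results. The antipsychotic summary is the output dedicated to that. If it is programmed as defined, it omits the drugs it exists to show. If it is programmed sensibly, the programmer has departed from the SAP without a written basis.

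**Working it through.** The plan states no figure on this point. The check sets the definition against the protocol and then counts who would be selected.

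**Inputs**

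- Planned size: 73 per arm in three arms, 3 × 73 = 219 (Protocol synopsis and section 7).
- Background antipsychotic at entry: required of every eligible subject (Protocol 8.1, criterion 5), so about 73 of 73 per arm.
- Approved drugs for CIAS: none (Protocol 4.2).
- Other candidates for a CIAS treatment: exclusion 28 in Protocol 8.2 bars "Use of off-label treatments for schizophrenia (including, but not limited to, donepezil and modafinil", and Protocol 11.4.1 lists cognitive remediation among prohibited treatments.
- Recorded data: Protocol 11.4.1 requires indication, daily dose, and start and stop dates for each concomitant treatment. Indication is therefore a field on which the SAP definition could be applied literally.

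**Selection under two readings**

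1. *By recorded indication, as the sentence is worded.* Let p be the fraction of subjects whose antipsychotic is recorded with CIAS as its indication. The summary then shows 219 × p subjects. If sites record schizophrenia or a symptom, p is about 0 and the count is about 0 of 219. The documents give no coding rule, so p is unknown. For illustration, p = 0.10 gives 219 × 0.10 = 21.9, about 22 subjects. Only p = 1 gives 219.
2. *By drug class, as the section title and the WHO coding suggest.* The count is about 73 of 73 per arm, or about 219 in all.

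The two readings can differ by up to the whole trial population. Nothing in 4.3.3 tells the programmer to use the second.

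**What the timing clause does**

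- An antipsychotic ongoing at entry and later re-dosed is still ongoing at entry, so the clause does not remove it.
- An antipsychotic first started on study falls outside the definition, but it meets the concomitant-medication definition in the same section and enters that by-arm summary.
- The missing-date rules in 4.3.3 are introduced as covering antipsychotic treatments as well as other therapies. One of them counts a therapy begun after the last dose. A treatment that must be ongoing at entry can never meet that rule, so the defined term is not used consistently within the section.

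**Where the variable is used**

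The models in SAP 4.4.1 to 4.4.3 adjust for combinations of treatment, visit, baseline and region. None of the readable primary or secondary models includes background antipsychotic treatment, so no treatment-effect estimate depends on this definition.

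**The case against.** The strongest reply is that this is a slip in one word and the intent is plain. The section title, the term being defined and the WHO coding all point to selection by drug class. A table with no antipsychotic users in a trial that requires one would be caught at once. The documents show neither form coding nor a programming specification, so a wrong table is possible but not certain. This stands as a limit on the consequence. It does not make the sentence right: a definition that works only when overridden should be corrected before it is used.

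Several stronger conclusions are tempting, and the documents do not support them.

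- *A reader might infer that on-study switches go unreported.* A new antipsychotic enters the by-arm concomitant-medication summary. SAP 4.1 also provides for data listings, and SAP 4.3.4 summarizes major protocol deviations by arm.
- *A reader might infer that restricting the table to drugs ongoing at entry is itself an error.* A background-therapy table may properly describe baseline use only, with later changes shown elsewhere.
- *A reader might infer that the missing-stop-date rule is a second error.* For a therapy begun before first dose, the SAP says that if "the stop date of that therapy is missing and the therapy is not listed as ongoing, the therapy will be considered non-concomitant". When both dates are missing, the therapy is counted as concomitant. The contrast is debatable, but the two records carry different information: in the first, nothing asserts that the drug continued. SAP 4.2 imputes partial dates, so only completely missing stop dates are at issue, and no frequency is given. It is a convention that the sponsor may wish to revisit, not a contradiction.

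**Conclusion.** The definition is wrong as written and should be corrected. The conclusion that it names the wrong indication rests only on the two documents. The size of the effect, about 0 subjects shown where about 219 are expected, rests on two assumptions: that selection follows recorded indication, and that sites do not record CIAS as the reason for the antipsychotic.

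The consequence is limited to one descriptive by-arm summary. Background drugs taken on study remain visible in the general concomitant-medication summary, and the primary and secondary efficacy analyses are unaffected. A reader might go further and suppose that an undetected background imbalance explains a treatment difference. Nothing in the documents indicates such an imbalance, and the treatment-effect estimate does not draw on this table.

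One real limit remains, and it is a gap in reporting rather than an error. Counts and percentages of users cannot separate a drug present at baseline from one added later, and cannot show a stop or a dose change.

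**What to change.** Replace the defining sentence in SAP 4.3.3 with: *Background antipsychotic treatment is any antipsychotic, by WHO drug class and regardless of recorded indication, that is ongoing at the date of first dose of study treatment.* Use the same term in the missing-date rules and in the closing sentence of the section. Anchoring on first dose also removes the undefined reference to trial entry. It keeps an antipsychotic first started on study from being labelled as background, which a definition based on any use on or after first dose would not do.

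Optional, as an addition and not a correction: a separate by-arm summary of subjects whose antipsychotic was started, stopped, or changed by more than the protocol's 25% limit after first dose. The protocol already treats larger changes as material, since "changes in background medication dosing that exceed this limit should be discussed with the Sponsor's Medical Monitor to determine subject disposition".

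The cost is one sentence of SAP text and the selection rule for one table, plus one table shell if the addition is adopted. Protocol 11.4.1 already requires the dose, date and indication data, so no new collection is needed.
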